App use. In the Habit app condition, descriptive statistics will be performed to summarize the number of days participants used each feature. These numbers will be inspected relative to the use targets defined for each feature. In the MyFitnessPal condition, descriptive statistics will be performed to summarize the mean number of days participants used MyFitnessPal over the 6-month intervention. A total “app compliance” score will be developed for each participant based on the percent of days they completed of their assigned use. Exploratory analyses using ANOVAs will compare conditions on app compliance scores at 6 months.

Retention. We will calculate retention as the proportion of participants who complete the 6-month follow-up assessment in each condition and report this information using a CONSORT diagram.

Engagement. Number of Facebook reactions (e.g., like, care, wow, etc.), replies, posts, and polls per participant during the 6-month program.

Acceptability. We will report participant satisfaction.

Burden. Using descriptive statistics, we will summarize burden scores in both treatment conditions. ANOVAs will be used to compare conditions on burden.

Group Cohesion. Using ANOVAs, we will compare conditions on group cohesion and climate total and subscale scores at 6 months.

Contamination. We will report the percent of participants that used any outside programs that provided weight loss coaching/problem solving.

Weight Change (exploratory). We will calculate weight changes from baseline to 6 months in each treatment condition. We will compare percent weight change from baseline to 6 months across the two treatment conditions using a mixed effects model approach with weight as the continuous outcome variable, and time as a covariate using percent weight change calculated from all available objectively measured weekly weights. To adjust for within-subject correlation in the mixed model, first we will estimate an unstructured within-subject covariance matrix; estimates may suggest that a simpler structure, e.g., compound symmetry (random intercept) is satisfactory.

Changes in weight loss problem solving. Using a mixed effects model with weight loss problem solving as the continuous outcome variable, we will compare conditions in change in weight loss problem solving from baseline to 6 months.

Group cohesion. Using ANOVA, we will compare conditions on group cohesion measures at 6 months.

Study Removal

Participants will be removed from the study if: 1) they do not complete all screening, baseline, and on-boarding procedures (two surveys, consent, webinar orientation, app set-up, and scale set-up, join the Facebook group), 2) become pregnant during the study period, 3) post inappropriate content in the Facebook group (e.g., bullying/harassment of others, hate speech, violent/graphic content, violating privacy of others etc.), and 4) if they choose to withdraw their participation from the study. Participants reporting that they would like to withdraw from the study will be given the option to 1) withdraw from all intervention-related activity and contacts, but still complete the final assessment or 2) withdraw from the study completely with no additional study contact. If a participant becomes pregnant during the study, they will be withdrawn from the intervention, but will be asked to complete the follow-up assessments.

Potential risks

Potential risks for being in this study includes injury while exercising, accidental exposure of personal information, and discomfort with study procedures (e.g., feeling uncomfortable

with some questions asked on a survey or answering in a focus group). The attempt to avoid risks to participants will be addressed by suggesting moderate intensity exercise to avoid discomfort, pain, or injury. Participants reporting discomfort will be told to go see their PCP. Injuries are unlikely to occur since we screen out medical conditions that could make someone prone to injury and we only suggest moderate activity. Moderate-level physical activity is 3.0 - <6.0 METs, which includes activities such as walking briskly (2.5 to 4 mph), playing doubles tennis, or pushing a lawn mower. To avoid accidental exposure of personal information, tracking data will be stored electronically in REDCap, a network secure data entry program, in the UConn-supported R drive, or OneDrive which is secure. Only those who have IRB approval to work on the study will have access to the R drive and REDCap database for this study. To avoid discomfort during study procedures, participants will be informed that they may withdraw from the study at any time if they feel discomfort with any of the study procedures or if they don't want to answer a question on a survey, they can skip it. Regarding the focus groups, they can request a one-on-one interview with study staff, or we can provide them with an alias in the focus group so others will not know who they are. The likelihood of each of these risks happening is rare since we take steps to prevent these from happening and if they were to happen, the severity would be likely be minor.

Potential Benefits

Participants may or may not benefit from participating in the study. Benefits that could occur are losing weight through the exercise and lifestyle changes and improvements in mental, physical, social, and emotional health. Through interacting with other participants and the counselor in the Facebook group, participants may also feel supported in their behavioral change efforts. Participants will also receive weighing scales that they are able to keep at the end of the study.

Societal benefits include providing evidence to support ways to help people achieve healthy lifestyle goals and improve the outcomes of their health in a way that could be less burdensome than other programs that are commercially available.

The possible risks of the study are minimal. If injury during exercise was to occur, it would likely be minimal because we screen out those at risk for injury or pain. Even then, injury can still happen, therefore we suggest moderate activity where injury is unlikely and/or would be minor (e.g., playing tennis may result in feeling minor pain/discomfort which should subside in a few days; and soreness may decrease over time as the body adjusts to the increase in movement). Any discomfort during the study can be mitigated because participants can stop participating or skip any questions they don't want to answer at any point. Focus groups can be done one-on-one or use an alias to hide their identity.

Accidental exposure of personal information is unlikely as steps are taken to prevent it (e.g., password protected UConn computers, only using secure websites or servers like the R drive and REDCap, only having approved personnel that are trained via CITI handle data). All these risks are outweighed by the possible benefits to participants (weight loss and enhancements in mental, physical, social, and emotional health) because it could improve their health and quality of life.

Costs to Participants

There is no cost to participants for participating in the study. Depending on smartphone data usage plan for each participant, usage charges may incur due to increased use of mobile apps.

Payment to Participants

Participants will be paid in the form of online Amazon gift cards. Participants will receive \$100 for completing the follow-up assessments which involve a weigh-in, survey, and focus group. The procedures for each assessment will need to be completed before providing compensation. Additionally, participants may keep the study scale provided to them.

For those that may be recruited via Qualtrics initial screening survey, whether they participate in this study or not, will receive Qualtrics incentives. Their incentives are based on a points system. Respondents accumulate points as they take surveys and then trade in points for E-gift cards to anywhere of their choice (amazon, walmart, target, etc.). The compensation Qualtrics provides is separate from the compensation for participating in the baseline and follow-ups of this trial.

Data Safety Monitoring

The Data and Safety Monitoring Plan will include monitoring the study for the progress of recruitment and retention, and the occurrence of adverse events (both serious and otherwise), inclusion/exclusion criteria, adherence to study protocols, and data review (completeness/outliers). Two safety officers will comprise the board.

I. Frequency of monitoring

During the pilot phase data reports will be reviewed and sent to the two safety officers once follow-ups have been completed and will include the following reports:

Recruitment rates and adherence to inclusion/exclusion criteria, and ethnic diversity goals:

Recruitment progress, including baseline characteristics, will be reviewed. This review will ensure that project deadlines are being met, that participants meet eligibility criteria, and that the ethnic diversity goals are being met. Recruitment progress is monitored weekly.

Adherence to study protocols:

Quality control will be conducted in all phases of the project. The Facebook group will be monitored daily for intervention protocol adherence.

Adverse events:

The adverse event report will include a listing of all adverse events including duration, severity, seriousness, relatedness, and action taken. Adverse events are documented throughout the intervention and at follow-up. In the event of a serious adverse event, the safety officers and IRB will be notified immediately.

Participant retention

Engagement will be tracked during the intervention, and completion of follow-ups will be documented. Participants will be reminded of upcoming study assessments. If a participant chooses to drop from the intervention, they will be given the option to skip the rest of the intervention, but still complete the follow-up. Retention is reviewed and discussed throughout the study and at follow-up.

Data review (completeness/outliers):

Data reports will be reviewed by the data manager, program director, statistician, and PI. Reports will include completeness of data; missing information within surveys; descriptive information for each endpoint without statistical testing; and quality control analyses for primary outcome. Data will be cleaned at the end of the study. A data review report will be provided to the IRB after the study is over and the team has time to create the report and sent off to the study sponsor (NIH).

II. AE reporting process

Baseline participants who report conditions that could create a safety concern while receiving the intervention will be excluded. Adverse events that occur during the intervention will be assessed, recorded, and followed. Safety monitoring procedures will be documented in a standard protocol and overseen by the PI and coordinator. Any adverse events will be immediately reviewed by the coordinator. The safety officers will be informed of all adverse events during data review. Serious adverse events will be communicated immediately to the PI and safety officers. The NIH and UConn IRB will be notified immediately in the event of serious adverse event. Any death of a study participant will be reported to the NIH and UConn IRB whether or not it appears to be related to the study.

III. Safety Monitoring Committee

The two safety officers for this project will include faculty independent from the research team with expertise in clinical psychology, exercise and weight loss interventions, and an understanding of the types and severity of injuries commonly experienced during weight loss trials. The two safety officers will review the reports sent by the project director will use a checklist to document any corrective actions that should be communicated to the principal investigators, the University of Connecticut IRB, and the NIH. In addition, the safety officers may include documentation on whether the principal investigators should provide follow-up to a participant.

Privacy and Confidentiality

For the initial screening survey, participants can answer the questions at their own place and in an environment of their choice since it is done via a link online. If they do not want to finish, they can exit out of the survey whenever they would like. We also provide a simple information sheet prior to the survey so they can decide if they even want to move forward with doing the screening survey.

During the webinar process, UConn staff will go over all the details of the study and what it means to be a participant to give them a thorough description of what they can expect and what the study is so they can decide if this study is a good fit for them. During the webinar, they turn their video and audio off and choose where they view the webinar.

Most contact is done online so participants can control where they are and how they answer on their own time. They will have ample time to decide if they want to participate or not and ask UConn staff any questions they may have. Consent will also be done online so they can control where they are when reading the form as well as the amount of time they have to read through the form before deciding.

Participants will be informed in the consent form that they are able to withdraw from the study at any time for any reason without any consequences. They can skip questions during baseline and follow-up assessments if it makes them uncomfortable as well.

The participant can control when, where, and how often they use the study apps and Facebook group. We will encourage them throughout the study to use each app and the Facebook group as directed, but we only do so when it seems like they may be falling behind and if they do not reply to our contacts, we do not bother them about it again.

Most communications are done on an individual basis to respect their privacy. For the webinar and focus group, they can request a one-on-one if they prefer, or we have alternate methods to help respect their privacy (e.g., turn off video/audio during webinar and use an alias during the focus group).

All communications and data collections are done only for necessary research purposes. Participants can specify preferred and non-preferred communication methods (e.g., calls, texts, emails) that staff will honor and only use non-preferred communication if needed (e.g., participant prefers phone calls, but staff needs to send a survey link, we would then email them).

Participants will likely interact with each other in the Facebook group and see each other's names and profile picture, but we make sure during the webinar and in the consent that

they are aware of that so all enrolled participants will be comfortable with sharing with others they may or may not know. Participants are free to change their Facebook name or profile picture if they wish. Any participants will be marked ineligible during screening/baseline if they do not wish to use Facebook for the study and any that become uncomfortable with it are free to withdraw at that point.

All data from participants is collected on an individual basis (aside from focus groups). Surveys are provided to them through secure links via REDCap that is unique to each participant.

The data will be maintained on UConn servers (R Drive, REDCap, and OneDrive) where security will be maintained through access controls. Files will be managed by the project coordinators, who will control user access and rights. For each user, REDCap will require a REDCap profile, username, and password to enter the program. Staff will only have access to the database, OneDrive, and R drive if the data manager or coordinator has given them access. The only staff who will have access to data are those approved on the IRB personnel and completed necessary CITI training. All participants will be assigned an ID number, which will link them to their study data. The ID number will be 2-4 numerical characters representing the number of participants in the study (e.g., the first person who fills out an eligibility screener would be ID 1). We will use Otter.ai transcription software to produce transcripts. Otter.ai retains no ownership rights to the recordings or transcripts. Staff will verify and edit the transcripts and then save the de-identified transcripts to the research drive on the UConn servers and delete the recordings from the drive and the Otter.ai platform. Please refer to these two sections of the terms of service and privacy policy: Terms of Service; Section 9 and specifically Section 9.3: <https://otter.ai/terms>: In summary, research team retains right to audio recordings and controls how the content is processed, transported, and distributed on the otter.ai platform. Once we delete the recordings from our trash, they are permanently deleted from platform. And from Section 2 of Privacy Policy: <https://blog.otter.ai/privacy-policy/> “We train our proprietary artificial intelligence technology on aggregated, de-identified audio recordings. Only with your explicit permission will we manually review certain audio recordings to further refine our model training data.”. PII fields will be stored in a REDCap form. Any data with PII in the R Drive will be minimal and only what is necessary for data management and analysis. It will be marked as such. Data will be completely de-identified once we have our master dataset saved in our R drive (which will be fully de-identified). At this time, the link between ID number and PII will be destroyed.

UConn IRB and their representatives as well as the study sponsor (NIH) will have access to the research data if requested.

Worcester Polytechnic Institute (WPI) will be able to see PII via the app use data that is entered into the Habit app that they can view on the backend. Additionally, study staff from WPI will join the Facebook group to assist participants with any Habit app issues. They all have had CITI training at WPI, will be approved personnel, and will not have a link to their study ID. Also, it is possible that participants in this study know each other.

Plans for data of participants who fail screening

The data collected from the screening will be stored in a form in REDCap under their study ID and will be kept until the end of the study. We will de-identify everything once we have the master dataset finalized.

Informed consent process

Participants will first read through a simplified information sheet prior to doing the eligibility screener. This will contain information about the study in general, next steps, and what data we will collect from them at this point. After reading through it, they will mark if they are or are not interested in participating in the study. If yes, they will go through the screening survey. From there, participants will then do an online webinar to learn more about the study and decide if this is a right for them, and then after that they will be sent the e-consent via a REDCap link where they will read through the consent form and consent online and then they will be sent a copy of the signed consent via email.

The research assistants/coordinators will by sending a link via email to obtain consent.

To be able to actively participate in the study, participants must be adults without impaired decision-making ability that are able to speak and read English. The webinar process prior to consent will include a discussion of the participants understanding of what participating in research means including their rights as a research participant, the protocol, as well as risks and potential benefits to participating in the study. If research personnel obtaining consent believes there is a concern regarding a participant understanding, participation will be discussed with the PI who will determine whether to exclude the participants on this basis.

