The total number of participants that will be enrolled into the 6-month feasibility trial is 70. It is estimated that we will screen ~1,700 participants to achieve this recruitment goal. Since the initial contact is via an online link, there will be many incomplete responses driving up the number of screened-out participants.

How was sample size determined?

We based the sample size of 70 for this pilot feasibility trial on necessities for examining feasibility. This sample size allows us to recruit online groups of 35 which we have demonstrated in an ongoing study is feasible and breeds regular engagement. Our previous work with smaller online groups (i.e., n=12)^{33,34} showed that presence of a few quiet participants can result in a fairly rapid decline engagement among entire group.^{33,34} We plan on enrolling waves of 70 participants (35 participants in each treatment condition), thus the feasibility trial allows to pilot recruitment procedures and assess feasibility of recruitment and engagement in the Facebook groups.

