Retention: With n=35 per treatment condition, the 95% confidence interval (CI) for the estimated retention rate in each condition will be within $\pm 11.8\%$ if the observed retention is 85%. Thus, given n=35 per condition, the lower limit of the 95% CI for the observed retention rate in either treatment condition should not be lower than 73.2%. App use: With n=35 per treatment condition, the lower limit of the 95% CI for observed proportion of 80% of participants meeting targets for app use in either treatment condition should not be lower than 66.7%. Acceptability: Assuming 85% retention, with n=30 available per treatment condition, the lower limit of the 95% CI for observed proportion of 80% of participants providing high acceptability ratings in either treatment condition should not be lower than 65.7%. Exploratory outcomes: We propose 6-month change in weight, 6-month change in weight loss problem solving, counselor time, and group cohesion at 6 months as exploratory because a true test of efficacy will require a fully powered trial informed by the refined procedures that will result from this feasibility study. Since the primary focus of this pilot trial is to assess feasibility to inform the design of the subsequent efficacy trial and the trial was powered to assess feasibility, not demonstrate efficacy, we only have 80% power to detect differences far larger than we expect to find in the subsequent efficacy trial. For example, taking an intent-to-treat approach, we have 80% power to detect differences of ≥ 0.68 SDs in weight change and the other exploratory outcomes. For example, if the SD=6.0%^{10,11} weight loss, we only have 80% power to detect differences in percent weight loss $\geq 4.1\%$, a difference 1.5-4 times larger than observed in previous research.

How are participants recruited?

Participants will be notified or approached about this research study through digital ads on various platforms (e.g., search engines, health websites, and social media platforms). One method we may use will be in collaboration with a company called Build Clinical. Build Clinical is a technology company that enables academic researchers to engage the exact populations needed for a given study.³⁸ Build Clinical will create the advertisements and landing page as well place the digital ads on the various platforms across the Internet. Participants will learn about the research study through these digital ads that will appear

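### The lower 95% confidence limits quoted for retention, app use and acceptability (73.2%, 66.7%, 65.7%) are Wald limits, 2.6 to 4.3 points above Wilson or exact limits, and the analysis names no interval for these proportions

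*Combined protocol and SAP*

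**What the plan says.** The figures stand under the heading on how the sample size was determined.

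- **Retention.** The paragraph opens "With n=35 per treatment condition, the 95% confidence interval (CI) for the estimated retention rate in each condition" and gives a half-width of 11.8 points "if the observed retention is 85" (percent). The next sentence concludes that "the lower limit of the 95% CI for the observed retention rate in either treatment condition should not be lower than 73.2" (percent).
- **App use.** With 35 per condition, the lower limit for an "observed proportion of 80% of participants meeting targets for app use in either treatment condition should not be lower than 66.7" (percent).
- **Acceptability.** With 30 per condition available after 85% retention, "the lower limit of the 95% CI for observed proportion of 80% of participants providing high acceptability ratings" is put at 65.7%.

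No interval method is named. In the Analytic Plan the retention entry reads "We will calculate retention as the proportion of participants who complete the 6-month follow-up assessment in each condition", reported in a CONSORT diagram. App use is summarised descriptively as days of use, and acceptability as participant satisfaction. None of these entries mentions a confidence interval.

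**The concern.** A symmetric interval of 11.8 points around 85% with 35 people suggests the simple normal-approximation (Wald) formula. With 30 to 35 people and a proportion well above one half, that formula centres the interval too high, so most of its error falls on the lower limit. The lower limit is the only one quoted for app use and acceptability, and it is the one from which the retention paragraph draws its conclusion.

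At stake is what the team takes from the pilot into the efficacy trial. The lower limit shows how low retention, app use or acceptability could still plausibly be, and a limit that is too high makes feasibility look better supported than it is. Because the Analytic Plan names no method, the final report could repeat the Wald calculation or give no interval at all.

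**Working it through.** **Inputs**, all from the sample-size section: retention p=0.85, n=35; app use p=0.80, n=35; acceptability p=0.80, n=30. The level is 95%, taken as two-sided (z=1.96), which the plus-or-minus half-width supports.

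**Step 1. Reproduce the stated limits.** Wald lower limit = p − z·√(p(1−p)/n).

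- Retention: 0.85 − 1.96·√(0.85·0.15/35) = 0.85 − 0.1183 = 73.17%
- App use: 0.80 − 1.96·√(0.80·0.20/35) = 0.80 − 0.1325 = 66.75%
- Acceptability: 0.80 − 1.96·√(0.80·0.20/30) = 0.80 − 0.1431 = 65.69%

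All three match the stated figures to within 0.05 point. The continuity-corrected Wald, Wilson, Agresti-Coull, Jeffreys and exact methods do not match.

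**Step 2. Limits by other methods.** Wilson: centre = (p + z²/2n)/(1 + z²/n); half-width = z·√(p(1−p)/n + z²/4n²)/(1 + z²/n). For retention, z²/n = 0.1098, so the centre is 0.9049/1.1098 = 81.5% and the half-width is 0.1304/1.1098 = 11.75 points. The interval is 69.8% to 93.3%. Exact (Clopper-Pearson) lower limit: the 2.5% quantile of Beta(np, n − np + 1).

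| Outcome | Stated | Wilson | Gap | Exact | Gap | Jeffreys | Gap |
|---|---|---|---|---|---|---|---|
| Retention | 73.2 | 69.8 | 3.4 | 68.9 | 4.3 | 70.6 | 2.6 |
| App use | 66.7 | 64.1 | 2.6 | 63.1 | 3.6 | 64.7 | 2.0 |
| Acceptability | 65.7 | 62.7 | 3.0 | 61.4 | 4.3 | 63.3 | 2.4 |

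Since 0.85 × 35 = 29.75 is not a whole number, the retention row is a planning value. At 30/35 the lower limits are Wald 74.1%, Wilson 70.6% and exact 69.7%. At 29/35 Wald gives 70.4% and Wilson 67.3%.

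**Step 3. Width.** Half-widths, Wald against Wilson: 11.8 and 11.7 points (retention), 13.3 and 12.9 (app use), 14.3 and 13.9 (acceptability). Exact half-widths are 12.9, 14.3 and 15.4. Wilson intervals are no wider than Wald; they sit lower.

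**Step 4. Coverage, by summing binomial probabilities.** At a true 85% with n=35, the Wald lower limit exceeds 85% when 33, 34 or 35 are retained: 0.0627 + 0.0209 + 0.0034 = 8.7%. The upper limit falls below 85% in a further 1.1%, so coverage is 90.2%.

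| True rate, n | Wald coverage | Lower limit above truth, Wald | Wilson coverage | Lower limit above truth, Wilson |
|---|---|---|---|---|
| 85%, 35 | 90.20% | 8.70% | 94.65% | 2.43% |
| 80%, 35 | 92.53% | 6.05% | 94.66% | 1.90% |
| 80%, 30 | 94.63% | 4.42% | 96.39% | 1.05% |

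The nominal value for the lower-limit error is 2.5%. Over all true rates from 80% to 85%, Wald coverage runs from 87.9% to 94.7% for n=35 (mean 91.9%) and from 85.5% to 94.7% for n=30 (mean 91.1%).

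**The case against.** The strongest reply is that there is no miscalculation. The three figures follow correctly from a textbook formula, they illustrate what 35 per condition yields, and nothing in the trial is decided by them. All of that stands. The fault is in the choice of method.

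A reader might infer more, in three ways that the documents do not support.

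- **That the basis for 70 participants falls.** The section states "The total number of participants that will be enrolled into the 6-month feasibility trial is 70" and grounds the number in feasibility needs and Facebook groups of 35, because smaller groups had lost engagement. The confidence limits describe what that size gives. No target precision is set that the corrected limits would miss.
- **That the intervals are too narrow.** Step 3 shows otherwise for Wilson. Only the exact interval is wider, by about 1 point.
- **That 73.2% is promised as a floor whatever retention turns out to be.** The preceding sentence conditions on an observed 85%, and the conclusion follows from it. The app-use and acceptability sentences carry their condition within them. How often a trial with a true rate of 85% would observe less than 85% is a separate question, which the plan does not address. The second retention sentence merely fails to repeat its condition.

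It is also fair to say that for acceptability the Wald coverage at the planning value (94.6%) is close to nominal. Even there the lower-limit error is 4.4% against 2.5%, and coverage at n=30 falls as low as 85.5% for other true rates between 80% and 85%.

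**Conclusion.** The point holds as one about where the lower limits are placed and how they are reported. The stated 95% lower limits are optimistic by 2.6 to 3.4 points against Wilson and by 3.6 to 4.3 points against exact limits (2.0 to 2.6 against Jeffreys). The shortfall in coverage is clearest for retention, smaller for app use, and slight for acceptability at its planning value. The sample size, the design and any decision within the trial are untouched.

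This rests on two-sided 95% intervals, on the plan's own planning proportions and denominators, and on participants in a condition being treated as independent, as the stated formula also assumes.

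**What to change.** **Sample-size section.** Restate the lower limits as about 70% (retention), 64% (app use) and 63% (acceptability), and name the Wilson method. Replace the symmetric 11.8-point half-width for retention by the interval, about 69.8% to 93.3% at an observed 85%. Repeat in the second retention sentence that the limit applies if the observed retention is 85%. If exact limits are preferred, the figures are about 69%, 63% and 61%.

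**Analytic Plan.** For each condition, report the proportion retained, the proportion meeting app-use targets and the proportion giving high acceptability ratings, each with a Wilson (or exact) 95% confidence interval. Use the same method as in the sample-size section.

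**Cost.** Wording only; the total of 70 stays. The stated lower limits become about 3 points less favourable with Wilson, and about 4 with exact limits.
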